3.2.10.3. Interim Analysis

An interim analysis will be conducted when we have enrolled 50% of the targeted 1020 patients, and completed 30-day follow-up on them. We will conduct an efficacy and futility analyses. For efficacy of clipping we will stop the trial if the two-sided p-value is less than 0.01. This alpha spending means that at the final analysis, a two-sided p-value less than 0.044 will be considered significant. At the interim look we will calculate the conditional power and terminate the study for futility if the conditional power is less than 20%. If the study will be continued, we will not modify the sample size based on the results of the interim analysis.

Because higher risk lesions may be more likely to benefit from clip closure the study should not continue to enroll patients if such benefit is apparent before study completion. We will therefore perform an interim safety sub-analysis for two groups of patients:

- (a) Patients with study polyps >4cm, and
- (b) Patients who are on anticoagulation or resume anticoagulation within 14 days of the polyp resection.

We assume that either group will contribute 10 to 20% to the study. We plan to conduct this safety analysis for each of these subgroups after 60 patients have been enrolled into either of the two subgroups (i.e. after enrollment of 60 patients with a >4cm study polyp and separately after enrollment of 60 patients who resumed anticoagulation after polyp resection). For example, the safety analysis would detect the occurrence of 2 vs. 9 delayed bleeding complications in the non-clip vs. the clip group as a significant difference (RR 4.5, 95% CI 1.01, 19.96). The study should cease to enroll these patients if the interim safety analysis shows a significantly increased relative risk in delayed bleeding complications in the non-clip group compared to the clip-group (see also Section on Monitoring).

A second safety analysis for these two groups will be part of the interim analysis after enrollment of 50% of patients (see above). Similarly, should this analysis show a significant difference in delayed bleeding complications, these patients should not be further enrolled.

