3.2.10. Statistical analysis

3.2.10.1. Primary analysis: Comparison between clip group vs. no-clip group, 30 day follow-up)

Primary endpoint: Delayed bleeding complication.

We will assess the null hypothesis that clipping has no effect on delayed bleeding complications using a chi-square test to compare the two study arms (as randomized, intention-to-treat), or a Fisher's exact test if appropriate with a 5% significance level.

Secondary endpoint: Overall complications.

The secondary endpoint will be compared between the clip and no-clip arms using a chi-square test (or Fisher's exact test if appropriate) with a 5% significance level.

The primary endpoint (delayed bleeding complication) and secondary endpoint (overall complications) are planned to be used to support clip-labeling plans.

The main analyses of the primary and secondary endpoints will be done on a per subject basis. Additional analysis will be conducted at the unit per polyp. Clustering of polyps within patients (estimated to occur in approximately 5%) will be accounted for by using the method generalized estimating equations as well as mixed-effects-analysis with a random intercept for patient.

Subgroup Analyses: While the study is not powered to look at subgroups we will conduct exploratory analyses to determine if any difference in the clip and no-clip arms is modified by characteristics such as time of occurrence (immediate vs. delayed) and by etiology (bleeding, perforation, etc.). This examination will be descriptive because the study will unlikely be sufficiently powered for identifying differences as significant.

Explorative analysis of the effect of electrocautery setting: The comparison between the two electrocautery settings (low power coagulation vs. Endocut) will be explorative. Pilot data show that one third of participating endoscopists typically use low power coagulation and two thirds use Endocut. Acknowledging a possible effect of cautery on the incidence of complications there is a need to standardizing the cautery setting for the EMR procedure. Rather than using one cautery setting for all procedures, the cautery setting will be standardized by randomizing patients to one or the other setting. At the same time this randomization will allow an explorative analysis of the effect of cautery on complications. This

information, although descriptive, would provide valuable guidance to develop resection standards.

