3.2.10.4. Sample Size Determination

Our sample size calculation is based on the primary aim. We hypothesize that polyp resection with clip closure of the mucosal defect will reduce the incidence of delayed bleeding complications. Prior studies have reported an overall bleeding incidence between 2 and 24% (table 1). We consider an absolute difference of 5% in delayed bleeding incidence (e.g. 8% and 3%) as clinically important. Assuming a two-sided alpha of 0.05 and a power of 80%, the study will need to include a total of 730 subjects (365 subjects into each group) to show such difference as significant. We assume that for approximately 20% of patients clip

closure will not be considered possible. Therefore approximately 920 patients will need to be included. However, approximately 10% of potential study polyps of referred patients will not meet inclusion criteria (screen failures). We estimate therefore that we need to enroll (=consent) a total of 1,020 patients for 920 patients to undergo the study intervention.

Because the primary outcome measure (delayed bleeding) will be assessed after 30 days of the colonoscopy we do not expect any dropouts.

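### The final test of the primary endpoint has two significance thresholds, 5% in Section 3.2.10.1 and two-sided 0.044 in Section 3.2.10.3, and the plan does not say which one decides

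*Combined protocol and SAP*

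**What the plan says.** Four parts of the protocol bear on the final threshold.

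- **Section 3.2.10.1 (primary analysis)** compares the arms as randomized on delayed bleeding by chi-square, "or a Fisher's exact test if appropriate with a 5% significance level". It does not mention an interim look. It adds that the primary endpoint is meant to support labelling of the clip.
- **Section 3.2.10.3 (interim analysis)** sets the timing: "An interim analysis will be conducted when we have enrolled 50% of the targeted 1020 patients, and completed 30-day follow-up on them". The efficacy rule is: "For efficacy of clipping we will stop the trial if the two-sided p-value is less than 0.01". The consequence is then given as: "This alpha spending means that at the final analysis, a two-sided p-value less than 0.044 will be considered significant". The section names no spending function or boundary method and does not state the overall alpha. It also says the study will "terminate the study for futility if the conditional power is less than 20" percent, without giving the effect assumed for conditional power or saying whether the rule is binding.
- **Section 3.2.10.4 (sample size)** gives the trial-wide level: "Assuming a two-sided alpha of 0.05 and a power of 80%, the study will need to include a total of 730 subjects".
- **Section 3.3.2 (DSMB)** repeats the 0.01 interim rule and gives no final level.

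Sections 3.2.10.1 and 3.2.10.3 do not refer to each other on this point.

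**The concern.** One confirmatory test has two written success criteria. Anyone working from the primary-analysis section alone would compare the final p-value with 0.05. Anyone working from the interim section would compare it with 0.044. For a result between the two, the trial's main conclusion would depend on which paragraph was followed. Section 3.2.5 says the study is not blinded and the result is intended for labelling, so the choice should not be left open until data exist.

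There is also a smaller question. The interim section presents 0.044 as following from the interim rule, so it should be reproducible from 0.01 at half information.

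**Working it through.** **Inputs.** Interim two-sided level 0.01, information fraction t = 510/1020 = 0.5, and final two-sided level 0.044 (Section 3.2.10.3). Alternative final level 0.05 (Section 3.2.10.1). Overall two-sided alpha 0.05, power 80%, rates 8% and 3% (Section 3.2.10.4).

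**Step 1: the plan's own sample size.** The two-proportion formula at two-sided 0.05 and 80% power for 8% versus 3% gives 326 per arm, and 365 per arm (730 in total) with continuity correction. This matches the plan and confirms that sizing used a single test at 0.05.

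**Step 2: the final level implied by the interim rule.** Under the null, the interim and final statistics Z1 and Z2 are approximately bivariate normal with correlation √t = √0.5 = 0.707. The overall error for a final level a is

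P(|Z1| ≥ 2.576 or |Z2| ≥ z(a/2)),

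where 2.576 is the critical value for two-sided 0.01. Setting this equal to 0.05 and solving gives a = 0.0452. The stated 0.044 is not reproduced. Other routes do not give it either:

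- Simple subtraction: 0.05 − 0.01 = 0.0400.
- Treating the looks as independent: 1 − 0.95/0.99 = 0.0404.
- One-sided 0.005 within 0.025, doubled: 0.0452.
- 0.044 would be exact at an information fraction of about 0.39, or for an interim level of about 0.0118 at t = 0.5.

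**Step 3: overall error under each candidate final level** (0.01 at t = 0.5, futility non-binding).

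| Final level | Critical value | Overall two-sided error |
|---|---|---|
| 0.044 (Section 3.2.10.3) | 2.014 | 0.0489 |
| 0.0452 (solved) | 2.003 | 0.0500 |
| 0.05 (Section 3.2.10.1) | 1.960 | 0.0546 |

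A simulation of 20 million null trials gave 0.0489, 0.0500 and 0.0546. A final test at 5% exceeds the design alpha by 0.0546 − 0.0500 = 0.0046, about half a percentage point. A final test at 0.044 leaves 0.0500 − 0.0489 = 0.0011 unused.

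**Step 4: sensitivity to the information fraction.** If the 510 patients at the look were all treated and are set against the 920 expected to undergo the intervention, t = 510/920 = 0.554. The solved level is then 0.0459, and 0.044 remains conservative with an overall error of 0.0482. A final 5% test would give 0.0539.

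**Step 5: power at 8% versus 3%.** With both looks counted, power rises from 83.7% at 0.044 to 84.0% at 0.0452 with 365 per arm, and from 91.1% to 91.3% with 460 per arm. The difference is 0.2 to 0.3 points.

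**The case against.** The best defence is that the two sections can be reconciled. The 5% in Section 3.2.10.1 equals the trial-wide alpha in Section 3.2.10.4, and Section 3.2.10.3 says explicitly what applies at the final analysis. If the specific rule governs the general one, the operative threshold is 0.044 and there is no inflation. This is a sensible reading, probably the intended one, but the text does not state it. Section 3.2.10.1 attaches its 5% to the test itself and does not call it an overall level.

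A second defence is futility stopping. If the rule were binding and conditional power were computed under the current trend, simulation gives an overall error of about 0.046 even with a 5% final test, and about 0.041 with 0.044. The plan specifies neither condition, so it cannot rely on this offset.

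A reader might go further and infer that 0.044 is an error that invalidates the analysis, or that neither threshold is usable. The documents do not support that. A prespecified level stricter than necessary controls the error, and nothing in the plan promises to spend exactly 0.05. The gap of 0.0452 − 0.044 = 0.0012 is also close to the resolution of the planned test, since a chi-square on a rare binary outcome is discrete. In simulated null trials with 365 per arm, the overall error at a 5.5% event rate was about 0.048 with either level. At an 8% rate it was 0.0489 with 0.044 and 0.0506 with 0.0452. Moving to 0.045 is therefore not essential, and it slightly relaxes the success criterion.

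**Conclusion.** The inconsistency is real and should be removed. Two thresholds are written for the final test of the primary endpoint, and they give opposite conclusions for a final p-value from 0.044 up to 0.05. Applying 5% after the 0.01 look at half information would take the overall two-sided error to about 0.0546.

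That figure depends on three assumptions: the 5% is used as the final nominal level, futility is non-binding, and the normal approximation holds at t = 0.5. It would be wrong to conclude that the plan as a whole inflates the error, because under Section 3.2.10.3 the overall error is 0.0489.

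The derivation of 0.044 is a minor, conservative imprecision. It does not follow from the stated interim rule, but it is valid and costs 0.2 to 0.3 points of power. This is a low-severity point, worth correcting because the ambiguity falls on the main decision rule and is easily removed.

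**What to change.** 1. In Section 3.2.10.1, for the primary endpoint, replace the 5% level with a reference to the single final threshold in Section 3.2.10.3.
2. In Section 3.2.10.3, state that the overall two-sided alpha is 0.05 and name the boundary method. Then do one of the following:
   - keep 0.044 and describe it as slightly conservative (overall error 0.0489 at 50% information); or
   - correct it to 0.045 (0.0452 at 50% information).

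Either choice settles the matter. Keeping 0.044 is the simpler edit and does not loosen the success criterion.

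The cost is a wording change in two sections. The sample size and data collection are unaffected, and the effect on power is negligible.

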3.1.4. Clipping and complication risk

It is apparent that resection of a large polyp leaves behind a large mucosal defect. The mucosal ulcer that forms after polyp resection can take several weeks to heal. Bleeding complication typically occur within 7 to 10 days, requiring often admission, a repeat

colonoscopy to stop bleeding, and possible blood transfusions. To reduce the risk of bleeding it has been proposed to close the mucosal defect after polyp resection.

To date, no randomized trial has examined whether clip application affects complications after large polyp resection. One recent study did not show a benefit²¹. Bleeding occurred in 2% in either group. However, the study included patients with smaller polyps (mean size 8mm) with a low expected bleeding risk. A recent retrospective study by Liaquat et al. showed that clip closure was associated with a significantly reduced risk of delayed bleeding (2% vs. 10%), and a reduced risk of overall complications (4% vs. 12%), when compared to historical controls²². Main limitations of the study include unmeasured factors that may have affected the outcome and performance of all resections by one expert colonoscopist. However, a third very recent retrospective study by Qumseya et al. reviewed their experience with 525 large colon polyp resection and did not find that clip closure was associated with delayed bleeding complications¹⁶.

In clinical practice use of clips after polyp resection is largely dependent on endoscopist preference and availability. In preparation for this study informal evaluation of polyp resection practice showed that some endoscopists use clips, and others do not. The unclear benefit with using clips, the required technical skills to achieve clip closure of the mucosal defect, and the additional cost may prevent some from using clips routinely.

Whether clip application prevents bleeding and other complications following resection of large polyps and may reduce overall cost of care remains an important clinical question: there is no established superior method, the issue arises daily, the potential impact on clinical practice from a definitive trial would be significant, both to establish an optimal approach and in terms of patient benefits.

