3.2.4. Patients on anticoagulation

Patients on anticoagulation medications will be managed according to the ASGE guideline²³. According to the guideline, polypectomy is considered a high-risk procedure. All study procedures are elective procedures. In accordance with the guideline, the type of anticoagulation and the patient risk for a thromboembolic event will determine the decision on managing periprocedural anticoagulation.

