3.2.5. Allocation to treatment (Randomization process)

Randomized will occur at the time of colonoscopy when a polyp has been identified as a study polyp using computer generated randomization. Patients will be randomized following a 2 x 2 factorial design to: (i) Endocut vs. low power coagulation after inspection of the polyp and decision to resect the polyp, and (i) clipping vs. no clipping of the mucosal defect after resection.

Patients will hence be randomized to one of four groups:

- A) Endocut and clipping,
- B) Endocut and no clipping,
- C) Low power coagulation and clipping, and
- D) Low power coagulation and no clipping.

Should a patient have more than one study polyp, all polyps will be resected in the same way (per patient randomization). The primary comparison will be between clip and no clip application. The comparison between cautery currents is secondary and exploratory.

Breaking the blind: The study is not blinded.

Treatment adherence/study compliance: The primary intervention (one-time clip placement) does not require adherence to the intervention. Participants will therefore not be excluded because of non-compliance.

The major outcome of interest will be assessed after 30 days following the intervention by a phone call. We expect that such short interval will allow an almost complete follow-up.

Secondary outcomes of interests include polyp recurrence during longer-term follow-up. We will collect data on all follow-up procedures that are performed as per standard of care (not as a study intervention).

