3.3.2. Data Safety Monitoring Board

- The DSMB consists of three independent gastroenterologists who are considered experts with respect to large polyp resection, and one statistician. After half of planned participating patients have been enrolled, the members of the DSMB will review all serious adverse events and review recruitment based on the proposed timeline.
- The study will be stopped should there be serious adverse events (bleeding, requiring additional interventions following the colonoscopy, perforation) related to study participation beyond what would be expected with respect to frequency or severity. The decision to stop the study will be made by the DSMB. The following stopping rules apply:
 - The study will be stopped should the interim analysis show a substantial difference between the clipping and non-clipping group of $p < 0.01$ (see Interim Analysis).
 - Patients with $>4\text{cm}$ polyps will no longer be enrolled should the interim safety subanalysis show a significant absolute difference in delayed bleeding complications between the clip and the non-clip group of at least 30% (see Interim Analysis).
 - Patients who are on anticoagulation or scheduled to resume anticoagulation within 14 days of a study polyp resection will no longer be enrolled should the interim safety subanalysis show a significant difference in delayed bleeding complications between the clip and the non-clip group (see Interim Analysis).

Research Materials. Data will be collected only if the subjects participate in the study. Data will be obtained only for research purposes.

Protection. Subjects will be afforded a variety of protections. First, all protocols will be IRB approved and subject to oversight by the local IRB. Second, once the data are collected they will be dealt with in an anonymous manner with adherence to HIPAA guidelines.

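### The anticoagulation safety subgroup is worded three ways, two of them using resumption after randomisation, so the interim safety look can lose early bleeds and power

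*Combined protocol and SAP*

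**What the plan says.** The protocol describes the anticoagulation subgroup in three places.

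- Analysis set (3.2.10.3, item b): "Patients who are on anticoagulation or resume anticoagulation within 14 days of the polyp resection".
- Trigger for the early look (3.2.10.3, in the parenthesis after the 60-patient rule): "separately after enrollment of 60 patients who resumed anticoagulation after polyp resection". This has no 14-day limit and no limb for patients who are on anticoagulation.
- Enrolment stop (3.3.2): "Patients who are on anticoagulation or scheduled to resume anticoagulation within 14 days of a study polyp resection will no longer be enrolled", should the look show a significant difference in delayed bleeding. This uses planned, not observed, resumption.

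Four other statements bear on the point.

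- Timing of allocation (3.2.5): "Randomized will occur at the time of colonoscopy when a polyp has been identified as a study polyp using computer generated randomization".
- Blinding (3.2.5): "The study is not blinded".
- Timing of bleeds (3.1.4): "Bleeding complication typically occur within 7 to 10 days".
- Management (3.2.4): decided patient by patient, since "the type of anticoagulation and the patient risk for a thromboembolic event will determine the decision on managing periprocedural anticoagulation". No resumption time is stated.

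Section 3.2.3 has medications reviewed before the procedure. The data list in 3.2.9.3 names neither anticoagulant use nor its planned or actual resumption.

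**The concern.** One rule decides whether a group of higher-risk patients may still be enrolled, and it rests on three different sets of patients. The DSMB cannot count to 60, analyse and act on the same group.

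Two of the wordings also use an event after randomisation. Bleeds are expected mainly in the first 7 to 10 days, inside the 14-day resumption window. A bleed can therefore come before resumption and prevent it. Where membership depends on having resumed, that patient and that event are not counted. In an open trial the decision to resume may also depend on whether the defect was clipped, and the subgroup comparison would then no longer be protected by randomisation.

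At stake is the sensitivity of a look whose stated purpose is to stop enrolling such patients once a benefit of clipping is apparent.

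**Working it through.** **1. The plan's own example.** Section 3.2.10.3 illustrates the look with 2 vs 9 bleeds, RR 4.5, 95% CI 1.01 to 19.96. Formula: SE of log RR = √(1/a − 1/n₁ + 1/b − 1/n₂), CI = RR × exp(±1.96 SE).

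- 60 per arm: √(1/2 − 1/60 + 1/9 − 1/60) = 0.760, CI 1.01 to 19.96. This matches the printed interval.
- 30 per arm, which is what 60 patients per subgroup gives with equal allocation: SE 0.738, CI 1.06 to 19.11.

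The printed interval thus needs 120 patients. The example also attaches the 9 bleeds to the clip group, the reverse of the decision rule. Both are separate matters. Below I use 30 per arm, with 2 bleeds in the clip arm and 9 in the no-clip arm.

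**2. How few lost bleeders matter in that example.**

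| Bleeders lost | Clip | No clip | RR (95% CI) | Fisher p | Chi-square p |
|---|---|---|---|---|---|
| none | 2/30 | 9/30 | 4.50 (1.06 to 19.11) | 0.042 | 0.020 |
| 1 no-clip | 2/30 | 8/29 | 4.14 (0.96 to 17.87) | 0.042 | 0.032 |
| 2 no-clip | 2/30 | 7/28 | 3.75 (0.85 to 16.55) | 0.075 | 0.054 |
| 3 no-clip | 2/30 | 6/27 | 3.33 (0.73 to 15.14) | 0.132 | 0.091 |
| 1 clip | 1/29 | 9/30 | 8.70 (1.18 to 64.41) | 0.012 | 0.007 |

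Unequal loss can move the RR either way.

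**3. Equal loss per bleeder.** If a share q of bleeders in each arm leaves the subgroup, a true risk p is observed as p(1 − q)/(1 − pq). With true risks 2/30 and 9/30 and 30 patients retained per arm:

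| q | Risk difference (points) | RR | Power, Fisher | Power, chi-square |
|---|---|---|---|---|
| 0 | 23.3 | 4.50 | 54% | 68% |
| 25% | 19.2 | 4.78 | 40% | 60% |
| 50% | 14.2 | 5.12 | 22% | 47% |
| 75% | 7.9 | 5.52 | 4% | 22% |

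The RR does not move toward 1. The loss is in events and power.

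**4. Linking q to timing.** All inputs here are assumptions: 30 per arm, all with the drug held; bleeding risk 25% no clip and 8% clip (true RR 25/8 = 3.1); bleed day lognormal with median 5 and sigma 0.7; resumption day uniform over a window; no resumption within 14 days after an earlier bleed. Then q is the average over the window of Φ((ln t − ln 5)/0.7). For days 2-7, q = 0.421, so no clip is 0.25 × 0.579/(1 − 0.25 × 0.421) = 16.2%, clip is 0.08 × 0.579/(1 − 0.08 × 0.421) = 4.8%, and RR is 3.4. Detection is the binomial probability of p < 0.05, with early bleeders removed and not replaced.

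| Resumption | q | No clip vs clip observed | RR | Chi-square | Fisher |
|---|---|---|---|---|---|
| no loss | 0 | 25% vs 8% | 3.1 | 44% | 29% |
| days 1-3 | 0.104 | 23% vs 7% | 3.2 | 41% | 29% |
| days 2-7 | 0.421 | 16% vs 5% | 3.4 | 28% | 21% |
| days 3-10 | 0.608 | 12% vs 3% | 3.5 | 19% | 13% |

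Waiting until 30 resumers per arm have accrued, as the trigger wording implies, does not restore detection: chi-square 32% and Fisher 13% for days 2-7, 22% and 5% for days 3-10.

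**The case against.** The formal definition has two limbs joined by an or. Being on anticoagulation can be read as status before the procedure, since medications are reviewed then, and on that reading a patient whose drug is held and who bleeds early stays in the subgroup. The count of resumers stands in a parenthesis and may be shorthand for item b. The enrolment stop in 3.3.2 already uses what can be known beforehand. All of this stands. It makes the loss of bleeders conditional on which wording governs, and the documents do not settle that.

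A reader might infer that the look is biased toward no difference. The documents do not support this. The rule in 3.2.10.3 is on the relative risk, and equal loss per bleeder leaves the RR slightly further from 1. Bias toward 1 needs greater proportional loss in the no-clip arm. That is plausible in an open trial, but nothing in the documents shows that clipping changes resumption.

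The size is also uncertain: early resumption costs almost nothing, and treating every member as held is close to a worst case.

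Finally, oversight does not rest on this look alone. Delayed bleeding is a serious adverse event (3.2.9.2) and the DSMB reviews all of these. There is a second subgroup look at 50% enrolment, but no separate definition is given for it, so it does not resolve the wording.

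**Conclusion.** The inconsistency is certain: the analysis set, the trigger and the enrolment stop name different patients, and the first two use actual resumption. The consequence is conditional. If the count of resumers governs, or if being on anticoagulation does not cover drugs held for the procedure, patients who bleed before resuming are lost with their events. Under the assumptions above, chi-square detection then falls from 44% to between 41% and 19%, with an observed RR of about 3.2 to 3.5 against a true 3.1. Those figures rest on assumed risks and on resumption timing that the documents do not give.

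Bias in the RR is a risk, not a finding. Nor should the point be carried over to the main result: the primary comparison in 3.2.10.1 is by intention to treat and keeps every bleed whether or not the patient resumed. What is affected is a safety look in a subgroup assumed to be 10 to 20% of the study, and the decision to go on enrolling it. The wording should be corrected, but the point does not threaten the trial's main conclusion.

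**What to change.** Align 3.2.10.3 with 3.3.2 through one definition based on information recorded before allocation: on anticoagulation at baseline, including patients whose drug is interrupted for the procedure, or resumption within 14 days planned. Use it for the 60-patient trigger, both safety looks and the enrolment stop. Keep every such patient in the subgroup whether or not the drug is in fact resumed, and report actual resumption descriptively only. Add baseline use, planned resumption and actual resumption to the data list in 3.2.9.3.

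The cost is a wording change, one pre-allocation entry on the CRF and a record of actual resumption. The downside is that some included patients will not in fact resume. The change concerns only who is counted; it says nothing about when anticoagulation should be resumed.

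### Sections 3.2.10.3 and 3.3.2 give different criteria for ending enrolment of patients with >4 cm polyps, and the plan's own worked example falls between them

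*Combined protocol and SAP*

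**What the plan says.** Section 3.2.10.3 (Interim Analysis) plans a safety sub-analysis in two subgroups: study polyps over 4 cm, and patients on or resuming anticoagulation. For the first subgroup the look comes "after enrollment of 60 patients with a >4cm study polyp". Enrolment of the subgroup should cease if the analysis "shows a significantly increased relative risk in delayed bleeding complications in the non-clip group compared to the clip-group". No minimum size of effect is given. The section illustrates what the analysis would detect with "2 vs. 9 delayed bleeding complications in the non-clip vs. the clip group as a significant difference (RR 4.5, 95% CI 1.01, 19.96". A second look comes at half enrolment: "Similarly, should this analysis show a significant difference in delayed bleeding complications, these patients should not be further enrolled". Again there is no minimum. On subgroup size: "We assume that either group will contribute 10 to 20% to the study".

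Section 3.3.2 (Data Safety Monitoring Board) introduces its list with "The following stopping rules apply". For polyps over 4 cm, enrolment ends should the sub-analysis "show a significant absolute difference in delayed bleeding complications between the clip and the non-clip group of at least 30" per cent. The bullet for the anticoagulation subgroup asks for a significant difference and has no such threshold. Each section refers to the other as if the two stated the same rule.

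**The concern.** The DSMB has two written criteria for one decision. One is on the relative scale and needs significance only. The other is on the absolute scale and needs significance plus a 30-point gap. A result that is significant but less than 30 points apart ends enrolment under one section and continues it under the other. This is a patient-protection rule for a subgroup expected to be 10 to 20% of the study, so the decision should not depend on which section is open.

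The 30-point threshold is also far from the plan's other figures. It requires a bleeding rate of at least 30% without clips, whereas the highest bleeding rate in Table 1 is 24.1% (that table is not specific to polyps over 4 cm).

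The worked example, which could have settled the meaning, does not. Read as labelled, it shows more bleeding with clips, and its interval does not correspond to 60 patients.

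**Working it through.** **Inputs.** Event counts 9 and 2, RR 4.5, interval 1.01 to 19.96, and a look at 60 patients in the subgroup (section 3.2.10.3); the 30% threshold (section 3.3.2). Assumptions: equal arms (9/2 = 4.5 requires this, and section 3.2.10.4 plans equal groups) and two-sided 5% (implied by the 95% interval).

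**Formulas,** for a non-clip and b clip bleeds with n per arm:
- RR = a/b; 95% interval = RR × exp(±1.96 × SE), SE = √(1/a − 1/n + 1/b − 1/n)
- chi-square without continuity correction = 2n(a − b)² / [(a + b)(2n − a − b)]; Fisher's test two-sided
- absolute difference = (a − b)/n

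**Reproducing the printed interval.**
- n = 60 (120 in total): SE = √(0.1111 + 0.5 − 0.0333) = 0.760, interval 1.01 to 19.96. This matches the print.
- n = 30 (60 in total): SE = √(0.1111 + 0.5 − 0.0667) = 0.738, interval 1.06 to 19.11. This does not match. A score interval, test-based intervals, a 0.5 correction, t critical values and unequal splits of 60 did not reproduce the print either.

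**Labels.** As printed (2 non-clip, 9 clip), non-clip over clip is 2/9 = 0.22. The rule looks for an excess without clips, and the section's stated reason is that higher-risk lesions may benefit from closure. In that direction RR 4.5 needs 9 non-clip and 2 clip bleeds.

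**Applying both criteria to 9 vs 2.**

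| | 30 per arm | 60 per arm |
|---|---|---|
| RR interval | 1.06 to 19.11 | 1.01 to 19.96 |
| Chi-square p | 0.020 | 0.027 |
| Fisher p | 0.042 | 0.053 |
| Absolute difference | 7/30 = 23.3 points | 7/60 = 11.7 points |
| 3.2.10.3 (by RR interval) | met | met |
| 3.3.2 (at least 30 points) | not met | not met |

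**Width of the conflict, with 2 clip bleeds.** A 30-point gap needs 0.30 × n more bleeds without clips: 9 more at n = 30, so 11; 18 more at n = 60, so 20. For the half-enrolment look, 510 patients can be read as treated, or as consented with about 920/2 = 460 treated; section 3.2.10.4 says "we need to enroll (=consent) a total of 1,020 patients for 920 patients to undergo the study intervention". Ten to 20% of these gives 46 to 102 patients in the subgroup. The last four rows apply only if the 30% bullet also governs that look, which section 3.3.2 leaves open.

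| Per arm | Basis | 3.3.2 met from | Opposite decisions on all three tests | On some tests only |
|---|---|---|---|---|
| 30 | 60 in total | 11 | 9–10 | 8 (chi-square) |
| 60 | size the printed interval fits | 20 | 10–19 | 9 (RR interval, chi-square); 8 (chi-square) |
| 23 | 10% of 460 | 9 | none | 8 (chi-square) |
| about 25 | 10% of 510 | 10 | 9 | 8 (chi-square) |
| 46 | 20% of 460 | 16 | 9–15 | 8 (chi-square) |
| 51 | 20% of 510 | 18 | 10–17 | 9 (RR interval, chi-square); 8 (chi-square) |

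The gap is not peculiar to 2 clip bleeds. At 30 per arm, results significant by Fisher's test but under 30 points exist for every clip count from 0 to 5, for example 6 to 8 against 0.

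**The case against.** The strongest reply is that the rules are layered: section 3.2.10.3 sends the reader to the monitoring section, which is later and more specific, also requires significance, and adds a minimum for polyps over 4 cm. A DSMB could apply both together. But section 3.2.10.3 states no minimum at either look, and the example it calls detectable is below 30 points at either arm size. The reading has to be supplied by the reader.

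Several narrower points stand in part.
- The example serves both subgroups, and the plan says only that the analysis would detect those counts as significant. It meets the relative-risk rule only once the labels are swapped. The two criteria differ without it.
- RR 4.5 also fits the printed labels as clip over non-clip. The reversal is inferred from the direction of the rule and its stated purpose, not from the ratio.
- Both intervals exclude 1, so the interval slip does not change the example's conclusion.
- At the stated 60 patients in total, only 9 and 10 conflict on all three tests. The wider ranges need 60 per arm or the larger half-enrolment subgroups.
- How often a conflict would arise depends on unstated rates. At 30 per arm with the sample-size rates (8% vs 3%), its probability is 0.1% by RR interval, 1.2% by Fisher and 10% by chi-square. With assumed rates of 20% vs 5% it is 9%, 18% and 40%.
- Section 3.2.10.1 names chi-square, or Fisher if appropriate, for the primary endpoint. At 9 vs 2 the expected count is 5.5 bleeds per arm, so a common convention would keep chi-square. The plan does not say that this choice carries over to the sub-analysis.

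**Conclusion.** The concern holds. The two sections state incompatible thresholds for the same enrolment decision, and on the plan's own illustration, with labels in the direction of the rule, one ends enrolment of patients with polyps over 4 cm and the other does not. This result rests on equal arms and a two-sided 5% level. It holds by the relative-risk interval and by chi-square at both possible denominators; by Fisher's test it holds at 30 per arm but not at 60.

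The label reversal and the mismatched interval are secondary errors. For the second, the slip could lie in the denominator used or in the stated timing of the look. The conflict concerns only the subgroup with polyps over 4 cm, and the primary analysis test is untouched.

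**What to change.** - Reconcile sections 3.2.10.3 and 3.3.2 so that one criterion for polyps over 4 cm, on one scale and with its direction stated, appears in both. Say whether it applies at both looks. The choice of criterion belongs to the sponsor and the DSMB.
- Relabel the example as 9 non-clip vs 2 clip.
- Make the example's interval agree with the look: 1.06 to 19.11 for 60 patients in total at 30 per arm, or keep 1.01 to 19.96 and state that the look is at 60 per arm.
- Name the test and level for the sub-analysis. Chi-square and Fisher disagree at 9 vs 2 with 60 per arm (0.027 vs 0.053) and at 8 vs 2 with 30 per arm (0.038 vs 0.080).

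The cost is wording in two sections, with no extra data or patients.
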